### 9.7.2 Sensitivity Analysis

Four sensitivity analyses will be conducted. For these analyses, in the interest of reducing the number of additional tables, only the descriptive statistics for the matched population ([Annex Table 2](#)), and primary results ([Annex Tables 4](#) and [5](#)) will be reported.

Two sensitivity analyses will be conducted to evaluate the robustness of the outcome definition:

1. Use of a 30-day Grace Period

Restrict the 60-day allowable grace period used to define the discontinuation outcome to 30 days to allow a gap of one month. This sensitivity analysis may be useful if the 60-day grace period is too lenient, as the usual day's supply of Stiolto is 30 days.

2. Use of a 90-day Grace Period

Since neither the Olodaterol/Tiotropium Bromide or Umeclidinium/Vilanterol drug products are available as generic formulations, the relatively high price of these medications may lead some patients to space out their doses to greater than the recommended dosing schedule or use one puff instead of two to prolong their medication supply. Patients may also neglect to take their medications due to forgetfulness or because they become less symptomatic. Thus, we will also increase the 60-day allowable grace period used to define the discontinuation outcome, to 90 days.

Two sensitivity analyses will be conducted in an attempt to increase the sample size:

3. Start Patient Identification Period in 21 May 2015

The primary identification period starts 180 days after Stiolto Respimat was approved by FDA for use in the US (21 May 2015) on 17 November 2015. This sensitivity cohort will start the patient identification period immediately upon FDA approval on 21 May 2015.

#### 4. Do Not Exclude Patients with Diagnosis of ACOS from the Cohort

Patients in the primary analysis with diagnosis of asthma (regardless of whether or not they have COPD) will be excluded to restrict to patients with only COPD. It is possible that some patients with COPD may have a claim for asthma prior to their COPD diagnosis as part of their COPD diagnostic work-up, rather than an ongoing asthma diagnosis. Therefore, this sensitivity cohort will not exclude patients with a previous diagnosis of asthma. Note that patients with only asthma but no COPD will still be excluded from this cohort.

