
Variables:
 
Exposures
 
 
• Olodaterol/Tiotropium Bromide (Stiolto®) delivered via Respimat inhaler
 
• Umeclidinium/Vilanterol (Anoro®) delivered via Ellipta Inhaler
 
 
Outcome
 
 
• Discontinuation of index treatment (Olodaterol/Tiotropium Bromide or Umeclidinium/Vilanterol), defined as persistence of treatment (no refill claim within 60 days (allowable grace period) after end of <n> days supply). Addition of another drug will not count as a discontinuation.
 
 
Covariates
 
Demographics
 
 
• Age on the cohort entry date
 
• Sex (Male, Female)
 
• Region (Northeast, North Central, South, West, Unknown, Missing)
 
• Insurance Type (Commercial, Medicare, Missing)
 
• Study Year of Cohort Entry (First Year: 17 Nov 2015-30 Nov 2016, Second Year: 01 Dec 2016-30 Nov 2017, Third Year: 01 Dec 2017-31 Mar 2018)
 
 
Concomitant Medications
 
 
• Oral Corticosteroids (OCS)
 
• Short acting muscarinic antagonist (SAMA)
 
• Short acting beta agonist (SABA)
 
• Long acting muscarinic antagonist (LAMA)
 
• Long acting beta agonist (LABA)
 
• Inhaled corticosteroid (ICS)
 
• LAMA / LABA combination (that is not Stiolto or Anoro)
 
• LABA / ICS combination
 
• LAMA / LABA / ICS combination
 
• NSAIDs
 
• Antihistamines
 
			

Name of company: Boehringer Ingelheim International GmbH			
Name of finished medicinal product: Stiolt® Respimat®; Anoro® Ellipta®			
Name of active ingredient: Olodaterol and Tiotropium Bromide (ATC R03AL06); Umeclidinium and Vilanterol (ATC R03AL03)			
Protocol date: 22 November 2019	Study number: 1237-0090	Version/Revision: 1.0	Version/Revision date: NA

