Name of finished medicinal product: Stiolto® Respimat®; Anoro® Ellipta®			
Name of active ingredient: Olodaterol and Tiotropium Bromide (ATC R03AL06); Umeclidinium and Vilanterol (ATC R03AL03)			
Protocol date: 22 November 2019	Study number: 1237-0090	Version/Revision: 1.0	Version/Revision date: NA

Cox proportional hazard regression model will be used to assess the relative rate (or hazard) of the outcome in patients treated with Olodaterol/Tiotropium Bromide compared to patients treated with Umeclidinium/Vilanterol during the one-year follow-up. Crude HRs and 95% CIs will be reported for the matched cohorts.
 
Among the matched cohort, relative risks with 95% CIs will also be reported, as assessed by conditional logistic regression.
 
Relative rates and risks will also be reported using standard multivariable regression.
 
Sensitivity Analyses
 
 
• Restrict the 60-day allowable grace period used to define the discontinuation outcome to 30 days.
 
• Increase the 60-day allowable grace period used to define the discontinuation outcome to 90 days.
 
• Start the patient identification period on 21 May 2015 immediately upon FDA approval.
 
• Exclude patients with ACOS. Patients with asthma only but not COPD are still excluded from cohort.
 
			
Milestones:	
 
- Feasibility assessment Sept 2018 (done)
 
- Draft study protocol Dec 2018
 
- Final study protocol Apr 2019
 
- Results tables available May 2019
 
- 1st Abstract submitted (ERS 2019, ISPOR or AMCP ) Jun 2019
 
- Manuscript submitted Q2 2019
 
		

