### **9.2 SETTING**

#### **9.2.1 Definitions**

Study Period: the period of time that includes the exclusion criteria assessment period, baseline, cohort entry date, and follow-up period for the study population. This period is the same for all patients.

The study period will be from 1 January 2008 to 31 March 2018, encompassing date of the earliest data availability to the date of the latest data availability.

Patient Selection Period: the period of time for which patients are eligible to enter the cohort. The earliest date of the patient selection period is 17 November 2015, corresponding to 180-days after US approval date of Stiolto Respimat.

Cohort Entry Date: Date of entry to the initial cohort of Stiolto or Anoro users.

[figure not shown]
Baseline Period: the 180-day period that ends 1 day prior to the cohort entry date used to assess covariate information. The baseline period will vary between patients depending on these dates. The earliest start of the baseline period would be 21 May 2015, the date of Stiolto approval (i.e. 180 days before November 17, 2015).

Follow-Up Period: the period of time between 1 day after the cohort entry date to the earliest occurrence of the outcome (discontinuation of refills), or any censoring criteria (365 days, death, disenrollment, or end of data). Addition of another treatment in addition to index treatment will not count as discontinuation.

For entry into the study population, patients will be required to have 180 days of continuous enrolment with both medical and pharmacy coverage. Data during the baseline period will be used to confirm study eligibility and classification of incident COPD. The follow-up period will be used for capturing first and second maintenance therapies. This is illustrated in **Figure 1**.

Figure 1

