## Study timeline for the Primary Study Population

## 9.2.2 Study population

The pre-matched study cohort will consist of patients initiating Olodaterol/Tiotropium Bromide or Umeclidinium/Vilanterol between 17 November 2015 and 31 March 2018.

The following exclusion criteria will then be applied:

Aged <40 years.

Enrolment with medical and pharmacy coverage prior to the cohort entry < 180 days.

Never had COPD diagnosis on the cohort entry date or prior to cohort entry.

A record for dispensed Olodaterol/Tiotropium Bromide delivered with Respimat inhalator or Umeclidinium/Vilanterol delivered with the Ellipta Inhaler during the 180-day baseline prior to cohort entry.

[figure not shown]
Diagnosis of asthma any time prior to cohort entry.

Diagnosis of lung cancer any time prior to cohort entry.

Diagnosis of lung transplant any time prior to cohort entry.

Figure 2

Below depicts the flow diagram of patients.

Diagnosis of COPD (ICD-9: 491.\*, 492.\*, 496.\*; ICD-10: J41.0, J41.1, J41.8, J42.\*, J43.0, J43.1, J43.2, J43.8, J43.9, J44.0, J44.1, J44.9) will be defined as the presence of an inpatient or outpatient claim.

Diagnosis of asthma (ICD-9: 493.\*; ICD-10: J45, J45.20, J45.21, J45.22, J45.90\*, J45.99\*) will be defined as either 1 inpatient claim or 2 outpatient events 30-365 days apart.

Diagnosis of lung cancer (ICD-9: 162.2, 162.3, 162.4, 162.5, 162.8, 162.9, 231.2; ICD-10: C34.00, C34.01, C34.02, C34.10, C34.11, C34.12, C34.2, C34.30, C34.31, C34.32, C34.80, C34.81, C34.82, C34.90, C34.91, C34.92, C7A.090, D02.20, D02.21, D02.22, Z85.118) will be defined as either 1 inpatient claim or 2 outpatient events 30-365 days apart.

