### Matched Cohort

A matched propensity score analysis will be used to assess comparative persistence between the two exposure comparison groups. Logistic regression will be used to calculate the propensity to initiate Olodaterol/Tiotropium Bromide versus Umeclidinium/Vilanterol given all covariates (except components of the Charlson Comorbidity index) listed in [section 9.3.3](#), according to the following model:

$$\text{Logit}(\text{Treatment} | X_1, X_2, \dots, X_n) = \beta_0 + \beta_1 * X_1 + \beta_2 * X_2 + \dots + \beta_n * X_n$$

Any covariates which are collinear with each other will be dropped from the analysis (if it causes failure of model to converge). The propensity score will then be used to identify up to 2 initiators of Umeclidinium/Vilanterol for each initiator of Olodaterol/Tiotropium Bromide with the same propensity score ( $\pm$  a caliper of 5%) as the corresponding initiator of Olodaterol/Tiotropium Bromide (Austin 2011).

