#### **Demographics**

- Age on index date
- Sex (Male, Female)
- Region (Northeast, North Central, South, West, Unknown, Missing)
- Insurance Type (Commercial, Medicare, Missing)
- Year of Cohort Entry (First Year, Second Year)

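### Sensitivity analyses 3 and 4 admit launch-period entrants and patients with prior asthma without adding either factor to the covariates, so residual confounding is possible and the planned tables have no row to show it

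*Combined protocol and SAP*

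**What the plan says.** The primary cohort excludes patients with "Diagnosis of asthma any time prior to cohort entry" (section 9.2.2). Its entry window is set in section 9.2.1: "The earliest date of the patient selection period is 17 November 2015, corresponding to 180-days after US approval date of Stiolto Respimat".

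The propensity score is estimated "given all covariates (except components of the Charlson Comorbidity index) listed in" section 9.3.3 (section 9.2.2, Matched Cohort). The multivariable Cox and logistic models in section 9.7.1.3 use the same list. The matched Cox model contains treatment only.

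Section 9.7.2 then changes the cohort twice:
- Item 3: "This sensitivity cohort will start the patient identification period immediately upon FDA approval on 21 May 2015".
- Item 4: "this sensitivity cohort will not exclude patients with a previous diagnosis of asthma". Patients with asthma but no COPD stay out.

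Reporting for all sensitivity analyses is limited to Annex 5 Table 2 for the matched population and Tables 4 and 5. No change to any model is stated.

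The documents disagree with themselves in two places that bear on this point:
- Section 9.3.3 gives "Year of Cohort Entry (First Year, Second Year", two levels without dates. The abstract gives three dated levels ("First Year: 17 Nov 2015-30 Nov 2016, Second Year: 01 Dec 2016-30 Nov 2017, Third Year: 01 Dec 2017-31 Mar 2018"), and the Table 2 shell uses the same three.
- The abstract describes analysis 4 the other way round: "Exclude patients with ACOS. Patients with asthma only but not COPD are still excluded from cohort".

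**The concern.** Leaving asthma out of the covariates is sound in the primary cohort, because patients meeting the asthma definition are removed. Analysis 4 lets them back in, and nothing in the text adds asthma to the score. The matched Cox model has no covariates, so an imbalance left after matching would pass straight into the hazard ratio. Table 2 has no asthma row, so the reader could not check for one.

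Analysis 3 has the same gap for calendar time. It adds the first 180 days after Stiolto was approved, when Anoro had been approved since December 2013 (section 7). The treatment mix could well differ in that window, but the dated entry-year levels start only when it ends.

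At stake is how these two analyses can be read. If the hazard ratio moves, the cause could be the larger cohort or an imbalance in the added factor. If it does not move, two effects may have cancelled.

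**Working it through.** **1. The plan's own figures.** 3,889 + 10,862 = 14,751, as in section 9.5. 21 May 2015 plus 180 days is 17 November 2015, as in section 9.2.1. Both reproduce.

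**2. Coverage of entry dates in analysis 3.** The three dated levels span 380, 365 and 121 days, 866 in total. The added window, 21 May to 16 November 2015, is 180 days, and none of them falls in a dated level. Share of the extended window: 180 / (180 + 866) = 180 / 1,046 = 17.2%. This is a share of days, not of patients. If the added days were absorbed into First Year, that level would grow from 380 to 560 days and would mix launch with later entry.

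**3. Where each factor could enter.**

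| Place | Prior asthma | Entry 21 May to 16 Nov 2015 |
|---|---|---|
| Section 9.3.3 list (propensity score, multivariable models) | absent | coding undefined: two undated levels |
| Abstract levels | absent | not covered |
| Matched Cox model | absent | absent |
| Table 2 | no row | no row |

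**4. Possible size, asthma.** The documents give no prevalence and no association with discontinuation, so every input here is an assumption. For a binary factor with prevalence p1 (Stiolto) and p0 (Anoro) and hazard ratio r for discontinuation, the treatment hazard ratio is multiplied by

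B = [1 + p1(r − 1)] / [1 + p0(r − 1)].

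Take p0 of 15% or 25%, a residual arm difference of 0, 2, 5 or 10 points, and r from 0.8 to 1.5.
- No difference: B = 1.00 for every r.
- p0 = 0.15, p1 = 0.17, r = 1.5: 1.085 / 1.075 = 1.009.
- p0 = 0.15, p1 = 0.25, r = 1.5: 1.125 / 1.075 = 1.047.
- p0 = 0.15, p1 = 0.25, r = 0.8: 0.950 / 0.970 = 0.979.

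**5. Possible size, launch entry, before matching.** Assume 1,500 to 3,066 added entrants; the upper figure is 14,751 / 866 × 180, that is, uniform accrual. Assume a Stiolto share of 2% to 10% among them, and r from 0.8 to 1.5. With 3,066 entrants and a 2% share, p1 = 61 / (3,889 + 61) = 0.016 and p0 = 3,005 / (10,862 + 3,005) = 0.217. Then B = 0.909 at r = 1.5 and 1.042 at r = 0.8, which are the extremes of the grid. If the launch share equals the main-window share, 3,889 / 14,751 = 26.4%, B = 1.00.

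**6. Precision, for scale.** Assume full 1:2 matching at the primary counts (3,889 to 7,778) and 50% to 70% discontinuing: 5,834 to 8,167 events. SE(log HR) = 1/√(events × 1/3 × 2/3) = 0.0278 to 0.0235, so the 95% CI is the hazard ratio multiplied and divided by about 1.05 to 1.06. With no true difference, the chance of a significant result is about Φ(|ln B|/SE − 1.96). This is 11% to 13% for a 2% bias and 42% to 55% for a 5% bias.

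**The case against.** A reader might infer that each analysis is confounded by exactly what it adds. The documents do not support that. Confounding needs a difference between arms and a link to discontinuation. The documents give neither, and without either one the factor B is 1.00.

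Other points on the same side:
- **Reuse of the covariate list is inferred.** Section 9.7.2 neither fixes nor changes the models. Reuse remains the natural reading, because the section points to the same table shells and section 9.8 commits to following the protocol strictly and documenting changes as amendments.
- **Proxies exist.** The score includes respiratory hospitalization, whose principal codes in Annex 4 include asthma codes, as well as ICS, LABA/ICS, oral corticosteroids, SABA and allergic rhinitis. They help only in part. The hospitalization item needs an inpatient principal diagnosis, and the drug classes are not specific to asthma in a COPD cohort. The covariate look-back is 180 days, while asthma history is taken from any earlier time.
- **The launch days are not certain to lack a level.** Section 9.3.3 has no dates, so they could be put into First Year. The missing-data rule in section 9.6 could also give them a level of their own, which would separate them, but only by accident. The plan does not say which.
- **A strong tie between launch period and treatment is not shown.** The approval dates make one plausible, but no launch-window shares are given.
- **The stated aim of analyses 3 and 4 is a larger sample.** Section 9.7.2 names robustness of the outcome definition only for analyses 1 and 2, and section 9.9 already concedes residual confounding in general terms. This lowers the stakes, but it does not make a known and recorded factor unmeasurable.

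**Conclusion.** The point holds as a gap in specification that leaves two sensitivity analyses open to residual confounding, not as demonstrated bias. On the natural reading, analysis 4 admits prior asthma with no asthma term, and analysis 3 adds 180 of 1,046 entry days that no dated level covers. The proxies are partial, the matched model cannot repair an imbalance, and Table 2 has no row for either factor.

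Size and direction are unknown. The illustrative ranges of 0.979 to 1.047 (asthma) and 0.909 to 1.042 (launch entry, before matching) rest entirely on assumed prevalences, shares and hazard ratios. They show only that a modest imbalance could be comparable with a confidence interval of about ×/÷ 1.05 to 1.06, which itself assumes 50% to 70% discontinuing. The primary estimate is not affected.

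The change is worth making before these analyses are run, because both factors can be built from data the study already uses.

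**What to change.** First reconcile two things:
- Section 9.3.3 with the abstract and Table 2 on the number and dates of the entry-year levels.
- The abstract with section 9.7.2 on analysis 4. As the abstract words it, the analysis would leave the primary cohort unchanged, since section 9.2.2 already excludes asthma. The asthma term below applies to the section 9.7.2 version.

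Then state the model for each analysis in section 9.7.2:
- **Item 4:** add a prior-asthma indicator, the same flag used for the section 9.2.2 exclusion, to the propensity score, the multivariable models and Table 2.
- **Item 3:** add an entry-period level for 21 May to 16 November 2015 to the same models and to Table 2.

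The cost is two sentences and two table rows, and the asthma flag already has to be built for the exclusion. There is a small downside: the flag may be noisy. Item 4 itself notes that some asthma claims may come from COPD work-up. The section 9.2.2 code list, as printed, also omits the J45.3, J45.4 and J45.5 groups, which Annex 4 lists under respiratory hospitalization. That code list should be checked at the same time.

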### 9.8 QUALITY CONTROL

will build measures for cohort inclusion, outcomes and covariates. Some of the measure algorithms will be based on those collaboratively developed for another respiratory-related protocol with clinical input from external pulmonology experts. When available, algorithms that have been validated in administrative databases will be used. When validated algorithms are not available, coding criteria will be based on clinical input and through searches of medical claim coding systems.

All measures created, cohorts developed, statistical analyses implemented, and tables completed will undergo quality control review by at least 1 additional analyst or scientist under the supervision of the senior scientist.

This protocol will be strictly followed in the study. However, measure definitions may undergo modification if determined to be scientifically sensible. All changes to this protocol will be documented in protocol amendments.

The study protocol has been written following the Code of Conduct by the European Network of Centres for Pharmacoepidemiology and Pharmacovigilance (ENCePP) [[R15-4870](#)] that provides a set of rules and principles for post-authorisation studies with regard to the best practices and transparency, thereby promoting scientific independence of such studies. The study will be registered to the ENCePP's E-register and the results will also be published on the same site.

The study protocol also follows the key elements of the Guideline for Good Pharmacoepidemiology Practices (GPP) by International Society for Pharmacoepidemiology [[R11-4318](#)], and the recent draft Guidance for Industry and FDA Staff “Best Practices for Conducting and Reporting Pharmacoepidemiologic Safety Studies Using Electronic Healthcare Data Sets” [[R15-4859](#)].

Quality controls include checks for the validity and logical content of codes and checks for missing values and variables. In order to control for potential inconsistencies and errors, all

variables will be tabulated. In addition, the distribution of each variable will be examined. Extreme observations with values larger than  $\pm 3$  standard deviations (SD) will be examined as potential outliers and consequently excluded from the dataset.

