## Handling of Missing Data

Missing data that occurs in covariates or descriptive variables will be classified as its own level. In addition, a feasibility assessment before beginning the analyses will be done, and variables with >75 % missing values will be excluded from all analyses, other than baseline characteristics. If a variable is left with only one level other than missing, the variable will be excluded completely from all analyses.

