Charlson-Deyo Comorbidity Index	
This measure computes a score by summing over the following components:
 
 
· If the event Acute Myocardial Infarction Occurs within 180 days, set the score to 1.0 Otherwise, set the score to 0.0
 
· If the event Heart Failure Occurs within 180 days, set the score to 1.0 Otherwise, set the score to 0.0
 
· If the event Peripheral Vascular Disease Occurs within 180 days, set the score to 1.0 Otherwise, set the score to 0.0
 
· If the event Cerebrovascular Disease Occurs within 180 days, set the score to 1.0 Otherwise, set the score to 0.0
 
· If the event Dementia Occurs within 180 days, set the score to 1.0 Otherwise, set the score to 0.0
 
· If the event Chronic Obstructive Pulmonary Disease Occurs within 180 days, set the score to 1.0 Otherwise, set the score to 0.0
 
· If the event Rheumatologic Disease Occurs within 180 days, set the score to 1.0 Otherwise, set the score to 0.0
 
· If the event Peptic Ulcer Disease Occurs within 180 days, set the score to 1.0 Otherwise, set the score to 0.0
 
· If the event Hemiplegia or Paraplegia Occurs within 180 days, set the score to 2.0 Otherwise, set the score to 0.0
 
· If the event Renal Disease Occurs within 180 days, set the score to 2.0 Otherwise, set the score to 0.0
 
· If the event HIV/AIDS Occurs within 180 days, set the score to 6.0 Otherwise, set the score to 0.0
 
· For the measure Cancer use the value of the measure as the score multiplied by weight 1.0 If the value is missing, set the score to 0.0
 
· For the measure Diabetes use the value of the measure as the score multiplied by weight 1.0 If the value is missing, set the score to 0.0
 
· For the measure Liver Disease use the value of the measure as the score multiplied by weight 1.0 If the value is missing, set the score to 0.0
 

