History of Hospitalization due to Respiratory Condition; n (%)			
Acute Myocardial Infarction; n (%)			
Angina Pectoris; n (%)			
Peripheral Vascular Disease; n (%)			

	Tio/Olo	Umech/Vi	Standardized Difference (95% CI)
Heart Failure; n (%)			
Hypertension; n (%)			
Upper Respiratory Tract Infection; n (%)			
Lower Respiratory Tract Infection; n (%)			
Cardiac Arrhythmias; n (%)			
Cerebrovascular Disease; n (%)			
All Cancers (except non-melanoma skin cancer); n (%)			
Allergic Rhinitis; n (%)			
Chronic Sinusitis; n (%)			
Bronchiectasis; n (%)			
Pneumonia; n (%)			
Chronic Bronchitis; n (%)			
Exertional Breathlessness; n (%)			
Anxiety; n (%)			
Dementia; n (%)			
Depression; n (%)			
Osteoporosis; n (%)			
Charlson-Deyo Comorbidity Index, continuous			
mean (sd)			
median [IQR]			
Charlson-Deyo Comorbidity Index, categorical			
0; n (%)			
1; n (%)			
2; n (%)			
3+; n (%)			
Acute Liver Injury or Failure; n (%)			
Chronic Kidney Disease (without ESRD); n (%)			
End Stage Renal Disease; n (%)			
Rheumatologic Disease; n (%)			

	Tio/Olo	Umecl/Vi	Standardized Difference (95% CI)
Peptic Ulcer Disease; n (%)			
Gastroesophageal reflux disease (GERD); n (%)			
Type 1 Diabetes Mellitus; n (%)			
Type 2 Diabetes Mellitus; n (%)			
Type 1 or Type 2 Diabetes with no chronic complications; n (%)			
Type 1 or Type 2 Diabetes with chronic complications; n (%)			
Mild Liver Disease; n (%)			
Moderate to Severe Liver Disease; n (%)			
Renal Disease; n (%)			
Metastatic Solid Tumor; n (%)			
HIV/AIDS; n (%)			
Hemiplegia or Paraplegia; n (%)			
Lifestyle			
Smoking Related Claim or Intervention; n (%)			
Vaccination for Influenza; n (%)			
Vaccination for Pneumococcus; n (%)			
Respiratory Function Procedures/Tests			
Pulmonary function tests; n (%)			
Six-minute walk test; n (%)			
Chest X-ray; n (%)			
Chest HRCT; n (%)			

*Tio/Olo, tiotropium/olodaterol; Umecl/Vi, umeclidinium, vilanterol.*

**Table 3.** Absolute Standardized Differences as Measured in the Unmatched vs. Matched Cohorts

	Abs. Std. Diff. (Unmatched)	Abs. Std. Diff. (Matched)	Change	Change (%)
Demographics				
Age on index date				
Gender				
Region				
Insurance Type				
Year of Cohort Entry				
Oral Corticosteroids; n (%)				
Short acting muscarinic antagonist (SAMA), n (%)				
Short acting beta agonist (SABA), n (%)				
Long acting muscarinic antagonist (LAMA), n (%)				
Long acting beta agonist (LABA), n (%)				

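### Section 9.8 excludes observations beyond 3 SD with no route for keeping a valid value and no unit of deletion; a minor companion point is the one-day rule for index fills recorded with zero days' supply

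*Combined protocol and SAP*

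**What the plan says.** **Outliers.** Section 9.8 says that all variables will be tabulated and "the distribution of each variable will be examined". Observations more than 3 SD out in either direction "will be examined as potential outliers and consequently excluded from the dataset". The same section commits to following the protocol strictly, provides for review by a second analyst, and adds: "However, measure definitions may undergo modification if determined to be scientifically sensible". Section 9.12 mentions basic plausibility checks for continuous variables such as age, without a threshold or an action.

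**Where removals could appear.** Neither the exclusion list in section 9.2.2 nor the attrition rows of Annex 5, Table 1 has an outlier step. Section 9.6 says: "Missing data that occurs in covariates or descriptive variables will be classified as its own level". It does not say whether a value deleted under 9.8 counts as missing.

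**Variables concerned.** Age and the Charlson-Deyo index are the covariates that Table 2 summarises with means and medians. The index has a row "Charlson-Deyo Comorbidity Index, continuous" and a second form with classes 0, 1, 2 and 3+. It enters the propensity model, because section 9.2.2 leaves out only its components; which form enters is not stated.

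**Days' supply.** Section 9.6 takes drug duration from the days' supply field and, unless otherwise noted, treats 0 as 1 day. No exception is noted for the two study inhalers. Section 9.7.2 gives 30 days as the usual supply of Stiolto. The primary outcome in 9.3.2.1 starts its 60-day grace period at the end of supply.

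**The concern.** The examination has only one stated result. The plan does not say what finding would let a correct but extreme value stay, so distance from the mean decides. On a right-skewed comorbidity score, the values beyond 3 SD are mostly real sick patients and not keying errors.

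The unit of deletion is also open, as is its timing relative to matching. Two competent programmers could build different analysis sets from the same sentence:

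- If patients are dropped, the study gains an eligibility restriction that is not listed in 9.2.2 or Table 1 and that trims high-comorbidity patients. The lower N in Tables 2, 4 and 5 would show the loss but not the reason.
- If only values are dropped, a true high score is recoded as missing.

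The days' supply rule has a similar character but less weight. It assigns a duration that conflicts with the plan's own usual supply, and end of supply drives the primary outcome.

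**Working it through.** **1. Cohort size.** Section 9.5: 3,889 + 10,862 = 14,751, which agrees with the stated total.

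**2. Roughly normal variable.** 2 × (1 − Φ(3)) = 0.0027; 0.0027 × 14,751 ≈ 40 observations flagged even when every value is correct.

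**3. A valid score that the rule can reach.** Annex 4: "If the event HIV/AIDS Occurs within 180 days, set the score to 6.0" and "If the event Chronic Obstructive Pulmonary Disease Occurs within 180 days, set the score to 1.0". A patient with both scores 6 + 1 = 7.

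**4. Charlson index, assumed distributions.** The documents give no distribution, so all of these are assumptions. The COPD point counts only within 180 days, whereas section 9.2.2 excludes only those who "Never had COPD diagnosis on the cohort entry date or prior to cohort entry". The share c scoring that point may therefore be below 100%. I took score = Bernoulli(c) + X, with

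- c = 0.5, 0.7, 0.9 or 1.0;
- X of mean 0.6, 0.8, 1.0, 1.2 or 1.4;
- X negative binomial of size 0.8, 1, 1.5, 2 or 5, or Poisson.

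That is 4 × 5 × 6 = 120 scenarios.

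One case in full, c = 0.7 and X negative binomial with mean 1.0 and size 1:

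- mean = 0.7 + 1.0 = 1.7
- variance = 0.7 × 0.3 + (1 + 1²/1) = 2.21, SD = 1.487
- cut = 1.7 + 3 × 1.487 = 6.16, so scores of 7 and above are excluded
- P(score ≥ 7) = 0.3 × (1/2)⁷ + 0.7 × (1/2)⁶ = 0.0133, and 0.0133 × 14,751 ≈ 196 patients

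Over all 120 scenarios:

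| Quantity | Range |
|---|---|
| Mean score | 1.1 to 2.4 |
| Share above mean + 3 SD | 0.25% to 2.57% |
| Patients of 14,751 | 36 to 379 |
| Lowest score excluded | 4 to 9 |
| Distance of score 7 from the mean, in SD | 2.34 to 6.97 |
| Scenarios with score 7 beyond 3 SD | 100 of 120 |

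**5. What value deletion does to the index.** By the Annex 4 definition the index is never missing: absent events and missing components score 0. A missing level for the index would therefore contain only the patients beyond 3 SD.

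**6. Zero days' supply.** Last persistent refill day = supply + grace period.

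| Grace period | True 30-day fill | Recorded 0, set to 1 |
|---|---|---|
| 60 days (primary) | 30 + 60 = 90 | 1 + 60 = 61 |
| 30 days | 30 + 30 = 60 | 1 + 30 = 31 |
| 90 days | 30 + 90 = 120 | 1 + 90 = 91 |

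Each limit falls by 29 days. In the primary analysis a refill on days 62 to 90 becomes a discontinuation; on-time monthly refills are unaffected.

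Per 1,000 zero-supply fills that are followed by a refill, if 2% to 10% of refills fall on days 62 to 90 (assumed), 20 to 100 become false events. If 30% to 70% of those patients would discontinue within 365 days anyway (assumed), event status changes for 20 × 0.3 = 6 up to 100 × 0.7 = 70. For the rest only the timing changes.

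Suppose such fills are equally common in both arms and add 1% false events to each. Let h₀ = −ln(1 − R₀), h₁ = 0.80 × h₀ and a = −ln(0.99) = 0.01005. Then (h₁ + a)/(h₀ + a) = 0.805, 0.803 and 0.802 for R₀ = 30%, 50% and 70%. A hazard ratio of 0.80 barely moves.

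**The case against.** The case for leaving the text alone has real force. Section 9.8 gives the purpose as control of inconsistencies and errors, and speaks of potential outliers. It can be read as a loosely worded review step. Its reach is narrow: nearly all covariates are yes/no or categorical, and if the Charlson index is screened only in its 0/1/2/3+ form, the score-of-7 example disappears. Trimming on a baseline covariate by one rule in both arms, before matching, narrows the population but does not by itself confound the comparison. Table 2 would still show balance among those kept. On the second point, claims in section 9.6 are adjudicated and paid, so zero-supply fills may be rare. The 30-day supply is stated for Stiolto only, and the grace-period analyses already probe refill timing.

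Most of this limits the consequence and does not remove the defect. Exclusion is still the only stated outcome, and neither second-analyst review nor freedom to modify measure definitions supplies a retention rule. The 90-day analysis tolerates refills on days 62 to 90, but it does not correct the primary result.

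Three stronger readings are tempting and unsupported:

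- *The rule deletes every patient with an uncommon comorbidity.* A positive on a 0/1 variable does lie beyond 3 SD when its prevalence is below 10%. But the plan refers to extreme observations and links plausibility checks to continuous variables, and such deletion would empty many planned rows of Table 2.
- *The hazard ratio is biased.* Nothing in the documents shows this, or a direction.
- *Value deletion defeats confounding control.* It loses detail, but by step 5 the missing level would mark very high comorbidity, which the propensity model can still balance.

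**Conclusion.** The outlier sentence should be changed. It is a stated rule that, if followed, removes legitimate extremes of age and of the Charlson-Deyo index in continuous form, and it leaves the unit of deletion to the programmer. With patient-level deletion the loss on the index is about 0.25% to 2.6%, resting wholly on the assumed distributions; the real figure could lie elsewhere. The harm is an undocumented restriction that trims high-comorbidity patients. With value-level deletion the harm is lost information. A distorted treatment comparison is not demonstrated in either case.

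The days' supply rule is a minor companion. The 29-day shift is exact for a true 30-day fill recorded as 0. The frequency of such fills and their split by arm are not given, and applying 30 days to Anoro is an assumption. The effect is probably small. A reader might infer that it favours one product; the documents give no basis for that.

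**What to change.** **Section 9.8.** Replace the closing clause that orders exclusion with: *Extremes are queried; only impossible values are corrected or set to missing; valid extremes and the patients who have them are kept; a patient whose age cannot be established is handled under the age criterion in 9.2.2.* If any patient is removed on this ground, add a row to Table 1 with the reason.

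**Section 9.6 (minor).** Do not apply the one-day rule to index-inhaler fills with a days' supply of 0. Use that product's modal non-zero days' supply in the data, and report the number of affected fills by arm.

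**Cost.** Two sentences, a few lines of code and one count by arm. A few mis-keyed but possible values may be kept, and some imputed durations will be wrong.
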